5.3 Treatment assignment

Randomization/Treatment numbers will be assigned to eligible subjects in Part 2 (see [Section 5.5.1](#) for details) prior to surgery. If provided, the Investigator will enter the randomization/treatment number onto the Electronic Case report Form (eCRF).

Patients in Part 1 will be enrolled sequentially across centers and will keep their screening/subject number throughout the trial. Patients in Part 2 will be randomized 2:1 to Arms 2A:2B.

The randomization/treatment numbers will be generated using the following procedure to ensure that treatment assignment is unbiased and concealed from subjects and Investigator staff, as applicable:

- For Part 1, the Investigator or his/her designee will contact the Sponsor at screening or baseline and confirm the subject fulfills the population criteria.
- For Part 2, IRT will be used. IRT is a validated system that automates the random assignment of treatment arms to randomization numbers in the specified ratio. The Investigator or his/her designee will log into the IRT system at screening or baseline and confirm that the subject fulfills the population criteria. The IRT will assign a randomization number to the patient, which will be used to link the patient to a treatment arm. Detailed instructions on the use of the IRT can be found in the separate IRT manual.

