9.4.2 Statistical model, hypothesis, and method of analysis

Handling of missing values/censoring/discontinuations

The primary analysis only considers the events “on treatment” (apply the window defined in [Section 9.4.1](#)), thus accounting for discontinuations from the randomized treatment arm or study.

Part 1

The number of patients with tBPAR is assumed to follow a binomial distribution, i.e.,

$r_i \sim \text{Binomial}(n_i, \theta_i)$, where r_i is the number of patients with tBPAR in treatment group i, n_i is the number of patients in treatment group i and θ_i is the probability of tBPAR.

Corporate Confidential Information

The posterior mean tBPAR rate will be presented together with the 95% credible interval.

Part 2

The number of patients with tBPAR is assumed to follow a binomial distribution, i.e.,

$r_i \sim \text{Binomial}(n_i, \theta_i)$, where r_i is the number of patients with tBPAR in treatment group i, n_i is the number of patients in treatment group i and θ_i is the probability of tBPAR.

The primary efficacy analysis for the first 3 months of Part 2 evaluates whether a CFZ533 treatment arm meets the pre-defined success criteria

Corporate Confidential Information

$\Pr(\theta_{CFZ5331} - \theta_{SOC} < 0.20 \mid \text{data}) > 60\%$.

The required posterior probabilities will be estimated from simulations of the posterior distributions of $\theta_{CFZ533} - \theta_{SOC}$ and compared to the thresholds for the levels of proof.

The prior distributions will be assumed to be a non-informative Beta(1/3,1/3) for CFZ533 and an informative prior of Beta(1, 13) for placebo. This informative prior corresponds to an approximate mean response rate of 7% with a 95% confidence interval of (0.2%, 24%) and was determined via a meta-analysis of control therapies (see [Section 9.6](#)).

The posterior mean tBPAR rates for each treatment group and for the difference in mean response rates between treatments will be presented together with 95% credible intervals.

Corporate Confidential Information

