9.5 Analysis of secondary and exploratory variables

9.5.1 Efficacy

Other efficacy variables will be analyzed similarly to the primary efficacy endpoint, although without the non-inferiority test:

- tBPAR at Months 3, 6 and 12
- BPAR at Months 3, 6 and 12
- Graft loss at Months 6 and 12
- Death at Months 6 and 12
- Graft loss or death at Months 6 and 12
- Antibody mediated tBPAR at Month 12

For each of the efficacy endpoints (primary and secondary), simple event rate estimates (proportion of events) will be obtained and each CFZ533 treatment arm event rate will be compared with the control arm event rates using Z-statistics based on two-sided 95% confidence intervals for differences in event rates.

As supportive analyses, BPAR and tBPAR will also be analyzed using the adjudicated results.

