These calculations assume that the primary efficacy variable, rate of tBPAR, follows a binomial distribution. The prior distribution for the control tBPAR rate, Beta(1, 13), is estimated from a Bayesian meta-analysis of tBPAR rates from four previous studies using a control treatment similar to the one used in this study. The four studies were selected from the studies used in a previous Novartis generated meta-analysis studies and are summarized in Table 9-1.

Table 9-1 Summary of historical control data

Study	Treatment	Number of patients with tBPAR	Total number of patients	tBPAR rate
1 - Vincenti et al 2007	B+Tac+MMF+CS	24	346	0.069
2 - Silva et al 2007	B+Tac XL+MMF+CS	17	214	0.079
3 - Silva et al 2007	B+Tac+MMF+CS	8	212	0.038
4 - Scholten et al 2006	B+Tac+ MMF(0.5g)+CS	4	63	0.063

B=basiliximab

Prediction of the control rate for a future trial resulting from the Bayesian meta-analysis is shown in Figure 9-3.

Figure 9-3 Results of Bayesian meta-analysis prediction

[figure not shown]

Figure 9-3 shows estimates of response rate and 95% credible intervals for each study based on study data alone (dashed lines) and from the meta-analysis (solid lines). The overall prediction for response rate in a future study is shown in red together with the mean and 95% credible interval from the posterior distributions and n^* , the prior number of observations that these data would contribute to a future analysis.

To allow for a simple randomization ratio for allocation of patients to treatment groups, it was decided to reduce the control arm to 15 patients, compared to 30 for the CFZ533 arms. Thus a prior beta distribution of Beta (1, 13) was chosen, which has a mean value of 7 with 95% CI (0.2, 24) and an approximate weight of 14 patients.

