6.2.3 Statistical model, assumptions and hypotheses

Graft loss, death, graft loss or death and antibody-treated biopsy proven acute rejections will be analyzed in a similar way to the tBPAR and time to tBPAR, although without the non-inferiority test. Other efficacy variables displayed in Table 6-1 will be presented within frequency tables to show the proportion of events and the CFZ533 treatment arm event rate will be compared with the control arm event rate using Z-statistics based on two-sided confidence intervals for differences in event rates.

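### The Z-statistic 95% intervals for event-rate differences do not hold their level at 30 versus 15 patients for rare, unequal rates, and have zero width when neither arm has an event

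*Protocol*

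**What the plan says.** Protocol 9.5.1 lists tBPAR, BPAR, graft loss, death, graft loss or death, and antibody-mediated tBPAR. It first says that these are analyzed like the primary endpoint, without the non-inferiority test. It then adds a frequentist comparison: "For each of the efficacy endpoints (primary and secondary), simple event rate estimates (proportion of events) will be obtained", and each CFZ533 rate is compared with control "using Z-statistics based on two-sided 95% confidence intervals for differences in event rates". The list includes "Graft loss at Months 6 and 12" and "Death at Months 6 and 12".

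SAP 6.2.3 splits the endpoints. Graft loss, death, graft loss or death, and antibody-treated BPAR follow the tBPAR and time-to-tBPAR analyses. The other efficacy variables, in a table that the public text does not show, are compared "using Z-statistics based on two-sided confidence intervals for differences in event rates". No confidence level appears there.

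On size, Protocol 9.6 says that "it was decided to reduce the control arm to 15 patients, compared to 30 for the CFZ533 arms", and Protocol 5.3 says "Patients in Part 2 will be randomized 2:1 to Arms 2A:2B".

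Neither document states a pooled or unpooled variance, a continuity correction, a score or exact alternative, or a rule for zero events.

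**The concern.** A Z-statistic interval for a difference in proportions relies on the normal approximation in both arms. With 15 control patients and rates of a few percent, one arm or both will often have no events. An empty arm then contributes nothing to the unpooled variance, and if both are empty the interval collapses to a point.

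Two misreadings are possible. A graft-loss or death difference printed as 0 with a 95% interval of 0 to 0 looks like precise equality, when 45 patients exclude very little. Conversely, a few CFZ533 events against an empty control arm can give an interval that excludes zero on weak evidence.

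**Working it through.** **Inputs**
- Arm sizes: 30 and 15 (Protocol 9.6).
- Level: two-sided 95%, z = 1.96 (Protocol 9.5.1).
- Control tBPAR: about 7% (Protocol 9.4.2). Protocol 9.6 uses an example of CFZ533 below 20% with control around 10%. I took CFZ533 10–20% and control 7–10% as the tBPAR-like range.
- Graft loss: Protocol 1.1 gives 95% first-year graft survival, so about 5%. The other rare rates, including those for death, are assumptions; I used 2–5%, and 5% versus 10% as an intermediate case.

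**Formulas** (p1 = x/30 for CFZ533, p2 = y/15 for control)
- Unpooled Wald: p1 − p2 ± 1.96 × √[p1(1−p1)/30 + p2(1−p2)/15].
- Pooled: the same with standard error √[p(1−p)(1/30 + 1/15)], p = (x+y)/45.
- Newcombe: combines the two single-arm Wilson limits.
- Exact coverage: the sum of the Binomial(30) × Binomial(15) probabilities over the 31 × 16 outcomes whose interval contains the true difference.

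**The stated level.** The 95% is not reproduced:

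| True rates, CFZ533 / control | Unpooled | Pooled | Newcombe |
|---|---|---|---|
| 10% / 7% | 91.9% | 94.1% | 97.1% |
| 10% / 10% | 91.3% | 96.4% | 97.9% |
| 20% / 7% | 92.6% | 96.9% | 97.0% |
| 20% / 10% | 92.7% | 97.1% | 96.9% |
| 5% / 10% | 78.6% | 92.6% | 98.2% |
| 5% / 2% | 82.9% | 78.4% | 99.1% |
| 2% / 5% | 68.8% | 72.6% | 99.7% |
| 5% / 5% | 96.9% | 96.1% | 99.0% |
| 3% / 3% | 99.2% | 97.0% | 99.6% |

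On a one-point grid over the whole tBPAR-like range, unpooled coverage runs from 88.9% to 94.6% and pooled from 94.1% to 97.4%.

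**Where the misses come from.** At 2% versus 5% the chance of no event in either arm is 0.98^30 × 0.95^15 = 25.3%. Each such trial reports 0 to 0 and misses the true difference of −3 points, which accounts for 25.3 of the 31.2 points of non-coverage. At equal rates the same 0-to-0 interval counts as covering the true difference of zero. That is part of why equal rare rates over-cover, and it says nothing about precision.

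**No events in either arm.** Every variance term is zero, so both Z forms give 0 to 0. The chance is 0.97^45 = 25.4% at 3% in both arms and 0.95^45 = 9.9% at 5%. For Newcombe, the Wilson upper limit for 0/n is z²/(n + z²): 3.84/33.84 = 11.4% for 0/30 and 3.84/18.84 = 20.4% for 0/15. The interval is −20.4 to +11.4 points. Miettinen-Nurminen gives −20.8 to +11.6.

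**Events in one arm only.** At a 7% control rate the chance of 0/15 is 0.93^15 = 34%. For 4/30 versus 0/15:
- Unpooled: 13.3 ± 1.96 × √(0.133 × 0.867/30), that is 13.3 ± 12.2, or +1.2 to +25.5 points, excluding zero.
- Pooled: −4.3 to +31.0.
- Newcombe: −8.6 to +29.7.
- Fisher's exact two-sided p = 0.28.

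**After the fix.** Over true rates of 1–40% in each arm, Newcombe coverage has a minimum of 94.3% and a mean of 96.0%; Miettinen-Nurminen 93.5% and 95.7%. Unpooled Wald has a minimum of 45.1% and a mean of 91.9%.

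**The case against.** The documents never say Wald. With a pooled standard error the shortfall at tBPAR-like rates disappears, and the 4/30 versus 0/15 interval includes zero. That stands, so the size at those rates depends on a variance form that the plan leaves open. It does not rescue rare, unequal rates or the zero-event case, where both forms fail. A continuity correction would remove the zero width (−5 to +5 points), but neither document mentions one.

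A reader might infer that these are the only frequentist comparisons of graft loss, death and rejection. The SAP does not support that. Section 6.1.4 gives tBPAR Kaplan-Meier estimates and a log-rank test, and 6.2.3 sends graft loss, death, their composite and antibody-treated BPAR to similar analyses. A zero-width interval would also probably not stand alone. Protocol 9.5.1 calls for analyses like the primary one, and if the primary priors were reused (an assumption), 0/30 versus 0/15 would give a credible interval of about −11.6 to +4.3 points. Still, the Protocol sentence applies the Z interval to every endpoint, and the SAP retains it for the variables not reassigned.

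No decision rests on these intervals: proof of concept uses the Bayesian posterior, and the tBPAR stopping rules use event counts. That stands and limits the weight of the point.

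**Conclusion.** The point holds for the reported secondary intervals. Read as unpooled Wald, coverage is about 89–95% at tBPAR-like rates and as low as 69% at 2% versus 5%. Pooling repairs the former but leaves 73% at 2% versus 5% and 78% at 5% versus 2%. Both forms give a zero-width interval when no events occur, with a chance of 25% at 3% in both arms and 10% at 5%.

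It would be wrong to conclude that coverage is always below 95%, since equal rare rates over-cover (97% at 5%, 99% at 3%), or that the proof-of-concept result is in doubt.

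The figures assume 30 and 15 analyzed patients and, except for first-year graft loss of about 5%, rare-event rates that the documents do not give. Modest changes in the analyzed numbers would not alter the conclusion.

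**What to change.** In SAP 6.2.3, replace the Z-statistic intervals with Newcombe hybrid-score or Miettinen-Nurminen two-sided 95% intervals for the risk difference. Choose one and state the 95% level. Make the same change in Protocol 9.5.1 at the next amendment. Settling this before analysis avoids choosing a method after zero cells have been seen.

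The cost is one sentence in each document and a standard software option, with no change to design or sample size. The intervals will generally be wider and look less favourable. The Protocol edit needs the usual amendment approvals, so it can wait for an amendment made for other reasons.

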9.5.2 Pharmacodynamics

Total soluble CD40 and total soluble CD154

These data will be summarized by treatment and subject. Descriptive statistics will also be provided such as mean, median, standard deviation, minimum and maximum, by time point and treatment.

9.5.3 Safety

Unless otherwise specified, safety analyses include all data collected, including after discontinuation of randomized treatment.

9.5.3.1 Main safety endpoint: estimated GFR using the MDRD formula

The key secondary and safety variable is renal function as assessed by eGFR (MDRD formula). This will be evaluated at Month 12 by comparing the mean eGFR values between groups.

The MDRD formula is defined as follows ([Levey et al 2003](#)):

$$\text{GFR } [\text{mL/min}/1.73\text{m}^2] = 186.3 * (\text{C}^{-1.154}) * (\text{A}^{-0.203}) * \text{G} * \text{R}$$

C is the serum concentration of creatinine [mg/dL]

A is age [years]

G=0.742 when gender is **female**, otherwise G=1

R=1.21 when race is **black**, otherwise R=1.

Local laboratory serum creatinine values will be used for all renal function data analysis. Serum creatinine results are in units of umol/L, so the following formula should be used to convert to the required unit of mg/dL:

$$\text{C}[\text{mg/dL}] = \text{serum concentration of creatinine } [\text{umol/L}] / 88.4.$$

Estimated GFR will be determined and summarized in each part of the study.

Handling of missing values/censoring/discontinuations

The analysis will be made on the FAS population. The following imputation method will be applied for patients with missing eGFR values:

- Patients that lose their graft will be assigned a value of zero for their missing GFR value.
- Patients that die or are lost to follow-up with a functioning graft will have an imputed value using the last-observation-carried-forward (LOCF) method.
- For patients that discontinue randomized treatment the eGFR will be considered missing after applying the windows defined in [Section 9.4.1](#).

Graft loss patients do not have a functioning graft; hence the lowest possible GFR value (zero) will be assigned to such patients. In contrast, patients that die with a functioning graft, die for different reasons (e.g., suicide, car accident, cancer). Similarly, patients who are lost to follow-up have renal function, but missing values for various reasons (e.g., moving from the area or not being able to make the site visit during the Month 6 or Month 12 visit window). Patients who have a functioning graft at the time of death or are Lost to Follow-up with a functioning graft will be analyzed via an imputation method that employs LOCF.

9.5.3.2 Other safety endpoints

Vital signs

All vital signs data will be listed by treatment, subject, and visit/time and if ranges are available, abnormalities (and relevant orthostatic changes) will be flagged. Summary statistics will be provided by treatment and visit/time.

ECG evaluations

All ECG data will be listed by treatment, subject and visit/time; abnormalities will be flagged. Summary statistics will be provided by treatment and visit/time.

Clinical laboratory evaluations

All laboratory data will be listed by treatment, subject, and visit/time and if normal ranges are available, abnormalities will be flagged. Summary statistics will be provided by treatment and visit/time.

Adverse events

All information obtained on AEs will be displayed by treatment and subject.

AEs and infections collected are to be coded with the MedDRA dictionary that gives preferred term and primary system organ class information. AEs and infection preferred terms are to be analyzed as a whole under the heading of AEs for each treatment arm. The incidence of AEs will be summarized by body system, severity and relationship to study drug by the following:

- AEs by primary SOC and PT
- AEs rated to have relationship to study drug by SOC and PT
- AEs by primary SOC, PT, and maximum severity
- SAEs by SOC and PT
- SAEs rated to have relationship to study drug by SOC and PT
- Deaths by SOC and PT
- AEs leading to discontinuation of a study drug by SOC and PT
- AEs leading to dose adjustment or interruptions of a study drug by SOC and PT
- infections by type of infection (viral, bacterial, fungal, and others) and microorganism of infection
- serious infections by type of infection and micro-organism of infection
- new onset diabetes mellitus (as defined in [Section 6.6.4.4](#))

- AEs by standardized MedDRA query (SMQ) levels (broad and narrow search)
- AEs by standardized MedDRA query (SMQ) and preferred term (broad and narrow search)

Multiple Occurrences for Tables:

In all tables about incidence rates of AEs / Infections, if a patient has multiple occurrences of an AE, this patient will be counted only once in the corresponding AE category. If a patient has multiple AEs within a system organ class, s/he will be counted only once for that class. If a patient has multiple severity ratings for an AE while on treatment, s/he is only counted under the maximum rating.

Information pertaining to AEs noted during the study will be listed by patient, including the verbatim term given by the Investigator, the PT and SOC given by the MedDRA dictionary, start and end date, causality, severity, and relationship to study drug as assessed by the Investigator.

BK-polyoma viremia and nephropathy

The following variables will be analyzed descriptively:

- occurrence of BK-polyoma viremia any time post-transplantation “on treatment”
- occurrence of BK-polyoma viremia any time after switching a patient to SoC treatment
- occurrence of BK-polyoma virus nephropathy any time post-transplantation “on treatment”
- occurrence of BK-polyoma viremia any time after switching a patient to SoC treatment.

The difference of the investigational regimens to the control regimen will be summarized by risk ratios and appropriate CIs.

EBV, CMV and TB

All EBV, CMV and TB surveillance data will be listed by treatment, subject, and visit/time and if normal ranges are available, abnormalities will be flagged. Summary statistics will be provided by treatment and visit/time.

Laboratory data

Abnormalities according to clinically notable criteria will be identified. A by-subject listing of individual subject laboratory data will be generated. Values outside of the clinically notable limits will be flagged. Shift tables describing changes from randomization/enrollment based on the clinical notable criteria will be presented.

Descriptive statistics (mean, standard deviation, minimum, median and maximum) of quantitative laboratory variables, including change from randomization/enrollment, will be generated by visit.

New onset diabetes mellitus (NODAT)

The incidence of subjects developing new onset diabetes mellitus after transplantation (NODAT) will be summarized by treatment group. The probabilities of developing NODAT will be compared between treatment groups at 6 and 12 months post-transplant using logistic regression models with HbA1c levels at randomization/enrollment as predictive variables. Death, graft loss, or loss to follow up without NODAT before Month 12 will not be counted as developing NODAT. This analysis will be performed using subjects in the FAS population who do not have DM at randomization/enrollment.

Corporate Confidential Information

9.5.4 Model based dose-exposure response analysis

Not applicable.

9.5.5 Pharmacokinetics

CFZ533 plasma concentration data will be listed by treatment, subject, and visit/sampling time point. Descriptive summary statistics will be provided by treatment and visit/sampling time point, including the frequency (n, %) of concentrations below the LLOQ, which will be reported as zero. Summary statistics will include mean (arithmetic and geometric), SD, CV (arithmetic and geometric), median, minimum and maximum. Concentrations below LLOQ will be treated as zero in summary statistics. A geometric mean will not be reported if the dataset includes zero values.

If data permit, PK parameters will be calculated as described in [Section 6.7.3](#) and will be listed by treatment and subject. Concentrations below the limit of quantification will not be considered for the calculation of PK parameters. Descriptive summary statistics will include mean (arithmetic and geometric), SD, and CV (arithmetic and geometric), median, minimum and maximum. An exception to this is Tmax where median, minimum and maximum will be presented.

A dose-independent, model-based analysis of IV and SC dosing may be used to determine the bioavailability of the SC administration in this study (see [Section 6.7.3](#) for more details). Also, any dose(concentration)-exposure relationship should be derived using same the approach. Such analysis will be reported in a separate standalone report.

9.5.6 Pharmacokinetic / pharmacodynamic interactions

The relationship between CFZ533 concentration (PK) and PD variables will be explored graphically. Modeling of PK/PD data using a population approach may be performed as appropriate and will be reported in a separate standalone report. The broad principles outlined in the FDA Guidance for Industry: Population Pharmacokinetics will be followed.

Drug-drug interactions

This study is also collecting data to document potential Therapeutic Protein Drug Interactions (TPDI) when CFZ533 is given in combination with mycophenolate mofetil and Tac in *de novo* kidney transplant patients.

To evaluate the potential for CFZ533 to cause TPDI via indirect (target binding) mechanisms, an exploratory population pharmacokinetic (PPK) approach may be conducted, aiming to identify unexpected TPDIs with planned co-therapies (monitoring trough concentrations of Tac and MPA), and to provide a first risk assessment in *de novo* transplant patients. This approach is aiming to evaluate CFZ533 (i) as a perpetrator, with potential interactions with drugs specific to the target indication (mycophenolate mofetil and Tac), or (ii) as a victim drug, treating concomitant medications as covariates, by assessing a drug interaction effect on clearance. This exploratory approach should be generating hypothesis, with findings to be confirmed through a prospective pooled PPK approach based on data collected in Phase III and Phase II, to ensure unbiased and conclusive analysis results.

Such exploratory analysis applying a population pharmacokinetic approach may be reported in a separate standalone modeling report.

Corporate Confidential Information

[figure not shown]
